### 2.1 Study Aims:

- 2.1.1 **Aim 1:** To assess treatment effectiveness, by comparing the proportions of participants in the Enhanced Usual Care (EUC) and Virtual Tobacco Treatment (VIT) study arms abstinent post enrollment.
- 2.1.2 **Aim 2:** To assess the potential effect of potential moderators (e.g., sociodemographics, medical and smoking history, cancer variables) on treatment effectiveness between the two arms.
- 2.1.3 **Aim 3:** To assess the processes of implementation and dissemination (acceptability, adoption, appropriateness, treatment fidelity, cost effectiveness, penetration/reach, and sustainability) of delivering tobacco treatment interventions at community oncology sites.

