## 9. Statistical Considerations

### 9.1 Estimated Effect Size

Based on our current trial preliminary findings (Preliminary Studies) and previous trial with low SES smokers, we conservatively estimate 7-day point-prevalence tobacco abstinence at 6-month follow-up will be 15% for the standard care group and 32% for the intervention group. This estimate is based on our current trial, which has a higher intensity control group.

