### 9.2 Power calculation:

#### 9.2.1 Aim 1. Primary effectiveness outcome.

The study will have 80% power to detect a 17% difference in 7-day point-prevalence tobacco abstinence with a two-sided significance level of 0.01 with 280 participants.

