#### **Numeric Results for Testing Two Proportions using the Z-Test with Unpooled Variance**

H0:  $P1 - P2 = 0$ . H1:  $P1 - P2 = D1 \neq 0$ .

Target	Actual	Diff						
		Power	Power* N1	N2	N	P1	P2	D1
0.80	0.80400	117	117	234	0.2700	0.1000	0.1700	0.0100
0.90	0.90042	148	148	296	0.2700	0.1000	0.1700	0.0100
0.80	0.80014	78	78	156	0.2700	0.1000	0.1700	0.0500
0.90	0.90167	105	105	210	0.2700	0.1000	0.1700	0.0500
0.80	0.80045	126	126	252	0.2900	0.1200	0.1700	0.0100
0.90	0.90130	161	161	322	0.2900	0.1200	0.1700	0.0100
0.80	0.80185	85	85	170	0.2900	0.1200	0.1700	0.0500
0.90	0.90186	114	114	228	0.2900	0.1200	0.1700	0.0500
0.80	0.80184	140	140	280	0.3200	0.1500	0.1700	0.0100
0.90	0.90061	178	178	356	0.3200	0.1500	0.1700	0.0100
0.80	0.80115	94	94	188	0.3200	0.1500	0.1700	0.0500
0.90	0.90119	126	126	252	0.3200	0.1500	0.1700	0.0500
0.80	0.80095	148	148	296	0.3400	0.1700	0.1700	0.0100
0.90	0.90146	189	189	378	0.3400	0.1700	0.1700	0.0100
0.80	0.80289	100	100	200	0.3400	0.1700	0.1700	0.0500
0.90	0.90024	133	133	266	0.3400	0.1700	0.1700	0.0500
0.80	0.80043	159	159	318	0.3700	0.2000	0.1700	0.0100
0.90	0.90101	203	203	406	0.3700	0.2000	0.1700	0.0100
0.80	0.80088	107	107	214	0.3700	0.2000	0.1700	0.0500
0.90	0.90015	143	143	286	0.3700	0.2000	0.1700	0.0500

\* Power was computed using the normal approximation method.

- 9.2.2 Aim 1. Secondary effectiveness outcome 1.  
For biochemically-confirmed 7-day point prevalence abstinence at 3-months, with a sample size of 140 in each arm then smallest detectable difference will be 18% with 80% power and a Bonferroni corrected alpha of 0.002 using and an estimated control rate of 20%.
- 9.2.3 Aim 1. Secondary effectiveness outcome 2.  
For self-reported 7-day point prevalence abstinence at 6-months, with a sample size of 140 in each arm then smallest detectable difference will be 22% with 80% power and a Bonferroni corrected alpha of 0.002 using and an estimated control rate of 31%.
- 9.2.4 Aim 1. Secondary effectiveness outcome 3.  
For self-reported 7-day point prevalence abstinence at 3-months, with a sample size of 140 in each arm then smallest detectable difference will be 22% with 80% power and a Bonferroni corrected alpha of 0.002 using and an estimated control rate of 28%.
- 9.2.5 Aim 1. Secondary effectiveness outcome 4.  

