For each of the 6, we will test the effects of these moderators listed above on the outcomes. We test the effects of these moderators in logistic regression models to determine their association with tobacco abstinence. Once a parsimonious multivariate model is developed, treatment arm will be included to test for the effect of the intervention on the moderators. Interactions between the treatment arm and the moderators will assess the relationship between the moderators and the treatment group on the effectiveness outcomes.

Also, GEE will be used to look at longitudinal models.

Multiple comparisons will be accounted for by considering Bonferroni adjustments.

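### Section 9.8.1 reduces the moderators on their pooled association with abstinence before arm enters, so effect modifiers with weak pooled association can be missed

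*Combined protocol and SAP*

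**What the plan says.** Section 2.1.2 states Aim 2 as "To assess the potential effect of potential moderators" on treatment effectiveness between the two arms. Section 2.4 classes this work as exploratory.

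Section 9.8.1 names six outcomes and a long list of factors, and then sets an order:

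1. Association with quitting: "We test the effects of these moderators in logistic regression models to determine their association with tobacco abstinence".
2. Reduction, followed by arm: "Once a parsimonious multivariate model is developed, treatment arm will be included to test for the effect of the intervention on the moderators".
3. Arm-by-moderator interactions, to assess how moderators and arm jointly relate to the effectiveness outcomes.
4. Multiplicity, for which Bonferroni adjustments are to be considered.

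The section gives no retention rule, no alpha and no number of tests. It does not say whether step 3 covers every listed factor or only those left after step 2.

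**The concern.** A moderator of treatment effect is defined by its interaction with arm. Steps 1 and 2 select on something else: whether the factor predicts quitting when the arms are combined. A factor that goes with more quitting under VIT and less under EUC can show no pooled association at all, and so leave the model before its interaction is examined. A factor that only predicts quitting stays in.

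At stake is what a null Aim 2 result means. For a factor removed at step 2, silence about its interaction would say nothing about moderation.

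The stated reason for adding arm is also misworded. Randomised arm cannot affect sex, age, years smoked or cancer type. For factors measured again at follow-up (Section 7.5, for example beliefs and cravings), an effect of arm is meaningful, but it belongs to a mediation analysis.

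**Working it through.** **The plan's own figure.** Section 9.1 assumes that abstinence "will be 15% for the standard care group and 32% for the intervention group". Section 9.2.1 states: "The study will have 80% power to detect a 17% difference", "with a two-sided significance level of 0.01 with 280 participants". The table is headed "Numeric Results for Testing Two Proportions using the Z-Test with Unpooled Variance". With that test,

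n per arm = (z₀.₉₉₅ + z₀.₈₀)² × [p₁(1−p₁) + p₂(1−p₂)] / (p₁−p₂)²
= (2.576 + 0.842)² × (0.32×0.68 + 0.15×0.85) / 0.17²
= 11.68 × 0.3451 / 0.0289 ≈ 139.5, so 140.

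Power at 140 per arm is 0.8018, against the stated 0.80184. The figure reproduces. Section 9.3 adds 28 patients, giving 308, or 154 per arm. Aim 2 has no power statement of its own.

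**Assumptions.** The documents give no subgroup rates, moderator prevalence, retention threshold or interaction alpha. The check assumes a binary moderator split 50/50, arm averages held at 15% and 32%, a screen between p<0.05 and p<0.20, and interaction alpha 0.05 without adjustment.

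**Method.** The simulation used 200,000 trials per scenario. The screen is a Wald test of moderator against abstinence, pooled over arms. The interaction is a Wald test of the difference between arms in the moderator's log odds ratio. Screened power counts trials that pass both.

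**Results at 140 per arm** (rates are level 0 / level 1; ranges run from the p<0.05 screen to the p<0.20 screen):

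| Pattern | EUC | VIT | Pooled | Interaction OR | Retained | Power, direct | Power, screened |
|---|---|---|---|---|---|---|---|
| A. Reversal, milder | 20/10% | 27/37% | 23.5/23.5% | 3.6 | 4-18% | 54% | 2-10% |
| B. Reversal, larger | 22/8% | 25/39% | 23.5/23.5% | 6.2 | 4-18% | 83% | 3-15% |
| C. VIT only, moderate | 15/15% | 22/42% | 18.5/28.5% | 2.6 | 50-76% | 34% | 17-26% |
| D. All benefit in one level | 15/15% | 15/49% | 15/32% | 5.4 | 93-99% | 78% | 72-76% |

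Example of the interaction odds ratio, pattern A: [(0.37/0.63)/(0.10/0.90)] / [(0.27/0.73)/(0.20/0.80)] = 5.29/1.48 = 3.6.

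**At 154 per arm:** B goes from 87% to 4-16%, C from 37% to 20-29%, and D from 81% to 77-81%.

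**Reading the table.** Screened power is close to retention times direct power: for C at p<0.05, 0.50 × 0.34 = 0.17; for D, 0.93 × 0.776 = 0.72. So in these scenarios passing the screen carries almost no information about whether the interaction would be found. The screen costs power in proportion to how often it removes the factor.

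**Limits of direct testing.** Expected quitters: 140 × (0.15 + 0.32) = 65.8, about 66. Counting the Section 9.8.1 list gives 22 factors of primary interest and 16 additional, 38 in all; 38 × 6 outcomes = 228 interaction tests. In pattern C at 154 per arm, direct power falls from 37% to about 5% with Bonferroni over 38 tests and to about 1% over 228. Screening first, then Bonferroni over an assumed 5 to 20 retained factors, gives 4-13%. In pattern B at the same size, direct testing over 38 keeps 37%, against 2-12% after the screen.

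**The case against.** **The exclusion is not written down.** The interaction sentence refers to the moderators, which could mean the whole list, and nothing says an omitted factor goes untested. This stands, and it is why the point is conditional. Under the wider reading, however, the reduction step does nothing for Aim 2 and the plan should say so. Either reading needs the same clarification.

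**Interactions are planned and the aim is exploratory.** Both are true. A reader might infer that Aim 2 goes unanswered or that the plan tests the wrong quantity altogether. The documents do not support that: the right quantity is named, and the doubt is which factors reach it. The primary and secondary analyses are unaffected. Exploratory status excuses low power, but it does not make pooled association a sensible filter for moderators.

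**The damage depends on the scenario.** This stands. The largest losses need pooled rates that cancel. A factor carrying all the benefit is nearly always kept.

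**Testing everything has a price.** This also stands. Under full Bonferroni, direct testing is no clear improvement in pattern C. The case for dropping the screen rests on complete, unselected estimates, not on more significant results.

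**The odd phrase is only wording.** Largely so, since the next sentence gives the intended interaction. It is still worth correcting, because the protocol lists moderators and mediators together.

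**Conclusion.** The point holds in conditional form. As written, Section 9.8.1 reduces the candidate moderators on association pooled over arms before arm or any interaction enters. If interactions then cover only retained factors, modifiers with weak pooled association can be missed. The loss is severe when the association reverses between arms, moderate when a modest modifier acts only under VIT, and small when one level carries all the benefit.

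It would be too strong to say that true modifiers are dropped as a rule: that follows neither from the text, which leaves the scope of the interaction tests open, nor from the figures, which vary widely by pattern. The sizes rest on the assumed subgroup rates, prevalence, screen thresholds and unadjusted alpha. With about 66 expected quitters, a null interaction would be weak evidence with or without the screen.

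**What to change.** In Section 9.8.1:

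- For each pre-listed baseline moderator, fit abstinence ~ arm + moderator + arm × moderator, with no prior screening on pooled association.
- Report every interaction estimate with its 95% CI, labelled exploratory. State the multiplicity rule and the number of tests it covers.
- Keep the parsimonious model only as a separate analysis of predictors of quitting.
- Replace the phrase about the intervention's effect on the moderators with a statement of the arm-by-moderator interaction. Keep effects of arm on re-measured factors for the mediation analysis.

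This changes the wording of the analysis plan and needs no new data. The cost is a longer set of estimates to report. Few interactions would survive a full Bonferroni adjustment, so the results should be read as estimates and not as significance tests.

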#### 9.8.2

Aim 3: To assess the processes of implementation and dissemination (acceptability, adoption, appropriateness, treatment fidelity, cost effectiveness, penetration/reach, and sustainability) of our intervention at community oncology sites.

To gain an initial understanding of implementation processes, for Aim 3 we will follow Proctor and colleagues' recommended taxonomy for measurement of implementation outcomes. Specifically, we will measure acceptability (satisfaction with content/delivery), adoption (program uptake), appropriateness (relevance), cost, and treatment fidelity/adaptation and penetration (reach) and sustainability. These implementation outcomes will be assessed with mixed methods using qualitative and quantitative data to be collected from patients, tobacco treatment counselors, NCORP oncology PIs and provider clinicians/staff, and EHR documentation.

We will use descriptive statistics to summarize implementation outcomes (Acceptability, Adoption, Appropriateness, Fidelity, Cost, Penetration and Sustainability) and conduct treatment group comparisons (i.e., Acceptability).

We will explore organizational readiness and site level engagement using existing quantitative and qualitative data respectively. In order to examine the generalizability of the study findings to the full NCORP network of cancer care delivery sites, we will use the most recent (2017) existing NCORP Landscape data to conduct preliminary analyses comparing participating and nonparticipating sites on relevant site characteristics.

	
9.8.2.1 Acceptability
 
Satisfaction with various aspects of the tobacco treatment program will be evaluated through participant survey responses and post-treatment interviews with a subset of patient participants. Patient Surveys. At the 6-month surveys, participant satisfaction will be assessed:
 

1 To what extent has the tobacco treatment program met your needs?;

2 How satisfied were you with the smoking cessation assistance received?;

3. How helpful was the smoking cessation assistance?;

4. Would you recommend this program?

 
Proportions of participants answering these questions will be compared between the arms using chi-squared tests.

Rev. Add3	
9.8.2.2 Adoption
 
Using the baseline, 12- and 36-month staff surveys, we will conduct paired t-tests and chi-square test to assess pre/post changes in organizational readiness (ORIC) and tobacco treatment delivery practices.

Rev. Add4	
9.8.2.3 Appropriateness
 
To measure perceived fit and relevance, we will report on the 12- and 36-month staff surveys and interviews of NCORP PIs, clinicians, and staff about the VIT's a) suitability, b) applicability, and c) match for their patients and site, as well as d) perceptions of site usual care content and implementation.

Rev. Add2	
9.8.2.4 Fidelity
 
We will evaluate the use and effectiveness of brief videos on enrollment using the Fisher's exact test: brief videos open (y/n) and enrollment (y/n). Using participant self-reported survey data, counselor process data, and quitline data, we will evaluate study treatment and non-study treatment (i.e., site-specific usual care, outside resources) utilization. We will dichotomize medication and counseling use into low vs. high (<math>\geq 8</math> weeks of NRT; <math>\geq 8</math> sessions) levels of treatment utilization. Within each group, we will use chi-square tests and ANOVAs to explore the association between participant characteristics and treatment utilization. We will use chi-square tests to compare the association of treatment utilization (brief videos open, level of medication and counseling use) on smoking outcomes. To predict smoking outcomes, we will use logistic regression models, which will include medication and counseling use levels, adjusting for confounders.

	
9.8.2.5 Cost

Rev. Add2  
Rev. Add3

We will calculate the incremental cost per quit of the intervention relative to EUC over the 6-month follow-up period as follows: (total per-person costs of intervention – total per-person costs of EUC)/(cessation rate with the intervention – cessation rate with EUC ). Cessation rates will be based on the primary outcome. Statistical uncertainty in cost and effectiveness inputs will be incorporated into the incremental cost per quit comparisons using Monte Carlo simulation methods allowing us to determine whether these ratios are significantly different from zero and allowing us to assess the proportion of simulation outcomes above or below relevant thresholds. The robustness of the cost-effectiveness ratio estimates will be further examined in sensitivity analyses in which each parameter is varied, singly and in combination, through plausible ranges. We will also generate “best case” and “worst case” analyses. Using Wilcoxon rank sum tests and trend tests (Cochran-Armitage), we will explore patient and site characteristics associated with implementation outcomes. We will also collect cost data on EUC components including staff time required to assess smoking status and refer current smokers to this tobacco treatment trial.

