At the 6-month survey (Supplemental Appendix C), participant satisfaction will be assessed using a mixture of multiple-choice question items: (1) To what extent has the tobacco treatment program met your needs? (2) Did you get the kind of smoking cessation assistance that you wanted; (3) How helpful was the smoking cessation assistance?; (4) How would you rate the quality of the assistance you received? (5) Would you recommend this program?; as well as open-ended free-text items about aspects of the program they found the most/least helpful, challenges faced to participation, and any recommendations for additional topics or programs that would have improved their experience at this time.

	6.2.3.1.2	
Semi-Structured Individual Patient Interviews
 
Following completion of their 6-month follow-up surveys, 40 intervention VIT participants will be randomly selected (based on smoking status) to participate in in-depth exit interviews. Using a semi-structured interview guide, study staff will conduct these virtual interviews. All participants will be asked open-ended questions about a) program engagement: (1) What did you think of the clinician video that you received encouraging you to enroll in the study?, (2) reasons for it being helpful or not; b) counseling: (1) What counseling components/NRT did you find the most helpful? Why?; (2) What counseling components/NRT did you find the least helpful? Why?; c) NRT medication dose and access: (1) Please tell me if you used any NRT medication. How much? How difficult/easy was it to access?; d) logistics and overall impressions: (1) What were some of the challenges you faced to participating?, (2) Probe: virtual assessments, mailed NRT, etc.; e) videoconferencing delivery: (1) Please tell me about your experience connecting with your tobacco counselor via a virtual screen. What did you like about it? Dislike about it? Difficulties to using the program? Benefits to using the program?; and f) cessation advice and assistance received from oncology care team.

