## 12. Electronic Data Capture

Please refer to the EAQ171CD Forms Completion Guidelines for the forms submission schedule. Data collection will be performed in Medidata Rave, EASEE-PRO, and REDCap.

This study will be monitored by the Clinical Data Update System (CDUS) version 3.0. Cumulative CDUS data will be submitted quarterly from the ECOG-ACRIN Operations Office – Boston to CTEP by electronic means.

**Patient individual and NCORP PI/Clinician/Staff Focus Group Interview Analyses:** Data analyses will occur coincident to data collection so that we can ascertain if thematic saturation (the point at which no new data are generated) has been achieved for each strata (treatment group, site). Interviews will be recorded, transcribed and analyzed using NVivo qualitative software. Content analyses will be conducted by the two RAs and overseen by Drs. [name] and [name]. The coders will meet to develop the thematic framework, categories, and coding plan. To ensure coding reliability, coding discrepancies will be resolved through discussion and comparison of raw data. Coding will continue until a high level of reliability (Kappa=>0.80) is established. Patient individual interview results will be analyzed by strata comparisons. NCORP site participants' focus group interviews will be analyzed according to appropriateness and feasibility.

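### Acceptability (exploratory Aim 3): the item lists disagree, graded answers would be better served by an ordered test, and the interview strata include an arm that is not interviewed

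*Combined protocol and SAP*

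**What the plan says.** Section 6.2.3.1.1 (Surveys) states that at 6 months "participant satisfaction will be assessed using a mixture of multiple-choice question items" and lists five: needs met, whether the patient got the assistance wanted ("Did you get the kind of smoking cessation assistance that you wanted"), helpfulness, quality ("How would you rate the quality of the assistance you received") and willingness to recommend. Free-text items follow. Response options are not given; the survey itself is Supplemental Appendix C, which is not among the documents.

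Section 9.8.2.1 (Acceptability) lists four items from the 6-month survey: needs met, overall satisfaction ("How satisfied were you with the smoking cessation assistance received"), helpfulness and willingness to recommend. The test is stated in one sentence: "Proportions of participants answering these questions will be compared between the arms using chi-squared tests". No coding, cut-point or significance level is attached.

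On interviews, Section 6.2.3.1.2 says that "40 intervention VIT participants will be randomly selected (based on smoking status) to participate in in-depth exit interviews". Section 12 (Electronic Data Capture), in a paragraph covering both patient interviews and staff focus groups, will check whether saturation "has been achieved for each strata (treatment group, site") and adds: "Patient individual interview results will be analyzed by strata comparisons".

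**The concern.** Section 2.4 defines acceptability as patients' satisfaction with the treatment they were assigned, and Section 9.8.2 singles it out as the implementation outcome for a treatment-group comparison. Three features of the plan stand in the way of a clean comparison.

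- The collection list and the analysis list cannot both describe the same survey. If the lists stay as they are, someone will have to decide after the data are in which items count.
- Several stems ask about extent, helpfulness, satisfaction or quality, which normally carry graded answers. A Pearson chi-squared test on three or more ordered categories spends its degrees of freedom on departures in every direction and so has less power against a general shift towards more or less satisfied. If the answers are instead to be dichotomised, the cut is left open.
- A comparison of patient interviews by treatment group needs interviews in both groups.

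**Working it through.** **1. Item lists side by side**

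| Item | Listed as collected (6.2.3.1.1) | Listed for arm comparison (9.8.2.1) |
|---|---|---|
| Needs met | yes | yes |
| Kind of assistance wanted | yes | no |
| How satisfied | no | yes |
| Helpfulness | yes | yes |
| Quality | yes | no |
| Recommend | yes | yes |

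Three items are in common. One is analysed but not listed as collected. Two are listed as collected but have no arm comparison.

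**2. Number of responders.** The plan states no sample size, power or alpha for acceptability. The only figure that fixes the available numbers is the primary-outcome size in Section 9.2.1. It reproduces with the unpooled formula named there: n = (2.576 + 0.842)² × (0.32×0.68 + 0.15×0.85) / 0.17² = 139.5, that is 140 per arm and 280 in total. The plan enrols 308 and expects about 28 deaths, leaving 280. Section 1.2.1 reports an 86% 6-month survey response in the earlier trial. 280 × 0.86 = 241, or about 120 responders per arm. Carrying that rate over to this trial is an assumption.

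**3. Power formulas.** Let p and q be the response distributions in the two arms, m their mean, n the number per arm and k the number of levels.

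- Pearson chi-squared: k − 1 df, noncentrality n × Σ[(p − m)²/m + (q − m)²/m].
- Wilcoxon or linear trend with midrank scores s: 1 df, noncentrality [Σ(q − p)s]² / (2·Var(s)/n), with Var(s) taken under m.

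Example with four equally likely levels in one arm and a common odds ratio of 2.0: p = (0.25, 0.25, 0.25, 0.25) and q = (0.143, 0.190, 0.267, 0.400). Both noncentralities come to 8.69. On 3 df at alpha 0.05 that gives 69% power; on 1 df it gives 84%. The signal is the same in both tests, and the loss is the cost of the extra degrees of freedom.

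**4. Results.** Assumed, not in the documents: 120 per arm, alpha 0.05, common odds ratio 2.0, and two response distributions for each number of levels above two.

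| Ordered levels | Chi-squared | Rank/trend test | Gain |
|---|---|---|---|
| 2 (yes/no) | 70% | 70% | 0 |
| 3 | 71–73% | 80–82% | about 9 points |
| 4 | 67–69% | 82–84% | 14–15 points |
| 5 | 62–66% | 82–85% | 19–20 points |

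A simulation of 4,000 trials (four levels, skewed distribution) gave 66.5% and 81.1%, against 66.7% and 81.7% from the formulas. With 110 to 140 per arm, the gain at alpha 0.05 runs from about 7–10 points (three levels) to 16–21 (five levels). At alpha 0.01 and 120 per arm it is about 11, 18 and 24 points for three, four and five levels.

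The advantage depends on a one-directional shift. For one non-monotone four-level pattern, (0.10, 0.20, 0.35, 0.35) against (0.20, 0.10, 0.30, 0.40), chi-squared has 70% power and the rank test 5%.

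**5. Interviews.** Section 6.2.3.1.2 selects 40 patients, all VIT, and the schedule in Section 7.3 shows exit interviews only in the VIT column. EUC interviews: 0. Site staff are not randomised, so the treatment-group stratum in Section 12 can apply only to patients, where it has a single level. Smoking status, the factor that drives selection, is not among the strata named there.

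**The case against.** The strongest reply is that graded answers are inferred, not documented. Section 6.2.3.1.1 says only that the items are multiple choice, and a comparison of proportions may mean dichotomised answers, for which chi-squared fits. That stands: a reader might infer that the plan applies the wrong test, but the documents show only that the coding is unstated, and chi-squared is valid in either case. Dichotomising does not settle the matter, though. In a five-level simulation at odds ratio 2.0 and 120 per arm, a split at the top two levels gave 76% power and at the top level alone 64%, against 84% for the rank test, and the plan fixes no cut. By contrast, Section 9.8.2.4 does state cut-points where it dichotomises treatment use.

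Other inferences also go further than the documents allow:

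- That the overall-satisfaction test has no data. The item may well be on the survey form, which is not available here.
- That the two unmatched items are lost. They are listed as collected, and Section 9.8.2 plans descriptive summaries of acceptability; what they lack is a named arm comparison.
- That the remaining comparisons are underpowered. The plan sets no effect size, alpha or power target for them, and a yes/no item loses nothing.
- That acceptability is the only Aim 3 outcome contrasted between arms. Section 9.8.2.5 also contrasts cost per quit.
- That the plan contradicts itself by using Wilcoxon and Cochran-Armitage tests in Section 9.8.2.5. Those serve a different purpose: patient and site characteristics associated with implementation outcomes.
- That the five-item list is the right one. Adopting it would drop the only item that asks about satisfaction directly, and the documents do not settle which list is correct.

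It can also be said that Section 12 does not spell out which strata apply to patients. It does name treatment group, however, and patients are the only participants who have one.

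**Conclusion.** The point holds as two internal contradictions and one conditional improvement, all confined to an exploratory outcome. The contradictions are certain from the text: the item lists agree on three items only, and a treatment-group comparison of patient interviews cannot be done with no EUC interviews. The improvement in the test is sound for any item with three or more ordered options and a shift in one direction. It is worth about 10, 15 and 20 points of power for three, four and five levels, and nothing for binary items. Those sizes rest on assumed values for responders, alpha, odds ratio and response distributions. The price is lower sensitivity to non-monotone differences, which matter less for a satisfaction scale. Primary and secondary conclusions are not touched.

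**What to change.** 1. Reconcile Sections 6.2.3.1.1 and 9.8.2.1 with the actual 6-month survey (Supplemental Appendix C), and compare arms on every satisfaction item that is asked.
2. In Section 9.8.2.1, state each item's response options, coding and significance level. For items with three or more ordered options, use a Wilcoxon rank-sum or trend test and report a proportional-odds ratio with confidence interval. Keep chi-squared for yes/no items.
3. In Section 12, for patient interviews, replace the treatment-group stratum with 6-month smoking status within VIT. Section 6.2.3.1.2 bases selection on smoking status after the 6-month survey.

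This changes wording only, with no new data collection. It should be done before acceptability data are examined by arm, so that neither the item list nor a cut-point can be chosen on the results.
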